5.1. Baseline Definitions

The Baseline value for statistical analyses is defined as the last evaluations prior to the first administration of investigational product in Study 977-311, unless otherwise specified. For subjects under protocol amendment 2, the baseline value is defined as the evaluations on Day 1.

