15.3. Safety Analysis

The LTSE Population will be the primary population used for safety analyses.

Safety data, including SAEs, TEAEs, physical examinations, ECGs, vital signs, clinical laboratory assessments, and treatment discontinuations, will be assessed.

The incidence of TEAEs and SAEs will be tabulated by system organ class, preferred term, and severity.

All events of potential hepatic injury, suspected liver-related clinical outcomes, and potential renal injury that occur after administration of the first dose of the investigational product will be reviewed and adjudicated by independent adjudication committees ([Section 14.3](#)).

Laboratory parameters and vital signs will be summarized (including Hy's law) using descriptive statistics at baseline (defined as the last assessment performed before the first dose of investigational product in Study 977-311) and at each scheduled post-baseline visit in Study 977-311. The change from baseline will also be summarized. ECGs will be summarized using frequency at each visit. The shift from baseline will also be summarized.

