15.3.2. Clinical Laboratory Evaluations

Laboratory parameters and vital signs will be summarized using descriptive statistics at baseline (defined as the last assessment performed before the first dose of investigational product in Study 977-311) and at each scheduled postbaseline visit. The change from baseline will also be summarized. ECGs will be summarized using frequency at each visit. The shift from baseline will also be summarized. Baseline is defined as the mean of all available evaluations before treatment (except for lipoprotein assessments where Baseline will be Day 1).

In addition, shift tables from baseline based on normal ranges will be provided for hematology, coagulation, and serum chemistry to assess changes in laboratory values from baseline (Day 1) to each evaluation through Month 60 (EOS) or ET.

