5. GENERAL CONSIDERATION

Individual subject data obtained from electronic case report forms (eCRFs), central and local laboratories, external sources, and any derived data will be presented in data listings by subject. All data listings that contain an evaluation date will contain a relative study day. Pre-treatment and on-treatment study days are numbered relative to the day of the first dose of investigational product which is designated as Day 1. The preceding day is Day -1, the day before that is Day -2, etc. The last day of investigational product is designated with an "L" (e.g., Day 14L). Post-treatment study days are numbered relative to the last dose and are designated as Day 1P, Day 2P, etc.

Tabulations will be produced for appropriate demographic, Baseline, efficacy, and safety parameters.

For categorical variables, summary tabulations of the number and percentage of subjects within each category (with a category for missing data) of the parameter will be presented. Percentage calculations will be based on non-missing data, unless otherwise specified. Percentages are rounded to 1 decimal place, unless otherwise specified.

For continuous variables, the number of subjects, mean, standard deviation (SD), standard error of the mean (SEM), median, minimum, and maximum values will be presented. The precision of summary statistics, unless otherwise specified will be as follows: mean and median to 1 more

decimal place than the raw data, and SD and SEM to 2 decimal places more than the raw data. In general, the decimal places should not exceed 3 decimal places unless appropriate.

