9.1. Efficacy Endpoints

The LTSE Population will be the population used for the efficacy analyses. Baseline is defined as the last assessment performed before the first dose of investigational product in Study 977-311, unless otherwise specified.

The efficacy endpoint at post-baseline site visits includes:

- Response rate of $\geq 40\%$ reduction from baseline and normalization rates of ALP
- Normalization rates of GGT, ALT, AST, total and conjugated bilirubin
- Change from baseline in GGT, ALT, ALP, AST, and total and conjugated bilirubin
- Percentage of subjects with ALP $< 1.67 \times \text{ULN}$, total bilirubin $\leq \text{ULN}$, and ALP decrease of $\geq 15\%$ from baseline
- Change from baseline in noninvasive markers of liver fibrosis, including liver stiffness measured by TE and ELF score
- Change from baseline in the GLOBE, UK-PBC, and MELD scores

All continuous and categorical additional endpoints will be summarized using descriptive statistics at baseline and at each scheduled post-baseline visit. No statistical inference will be done on those endpoints.

[figure not shown]
The intercurrent event in this study includes the use of prohibited medication and treatment discontinuation. Data collected after the intercurrent events, such as the use of prohibited medications, and data collected after treatment discontinuation will be included in the analyses (Treatment Policy Estimand).

The 5 attributes of the efficacy estimand are provided in Table 1.

[figure not shown]
Table 1: Attributes of Efficacy Estimand

[figure not shown]
Estimand Attribute	Elements
Population	All subjects with PBC who participated and are actively taking investigational product in Study 747-213 or Study 747-214 (or other Sponsor studies)
Treatment	OCA+BZF FDC Tablets
Efficacy Endpoint	All efficacy endpoints
Intercurrent Events	Use of Prohibited medication (Treatment Policy) Treatment Discontinuation (Treatment Policy)
Primary Efficacy Endpoint Population Level Summary	Descriptive summary in the target population

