10.3. Clinical Laboratory Evaluations

Laboratory parameters will be summarized in both conventional and standard international system of units using descriptive statistics at Baseline and at each on-study evaluation. Baseline is defined as the mean of all available evaluations prior to the first administration of investigational product.

The normal ranges of the selected lab parameters are defined below. The abnormal indicators of the selected lab parameters will be derived based on these normal ranges (inclusively):

- ALP 44-122 U/L
- ALT 0-45 U/L
- AST 0-45 IU/L
- GGT 0-65 IU/L (male) 0-60 IU/L (female)
- Total Bilirubin 1.71-12.3 umol/L
- Direct Bilirubin 0-0.4 mg/dL
- Cholesterol 0-169 mg/dL (age ≤19), 0-199 mg/dL (age >19)
- LDL 0-109 mg/dL (age ≤19), 0-99 mg/dL (age >19)
- HDL >39 mg/dL
- Creatinine 0.57-1.27 mg/dL
- Creatine 0.0-0.7 mg/dL (male) 0.1-1.0 mg/dL (female)
- CK 41-439 U/L (male, age 18-50 years old), 41-331 U/L (male, age 51-80 years old),

32-182 (female, age 18-80 years old)

For the other lab parameters, the normal ranges and abnormal indicators are based on the values in the data from the central or local labs.

In addition, shift tables (i.e., low-normal-high at Baseline versus low-normal-high at post-Baseline visit in a 3-by-3 contingency table) from Baseline to worst value, last value, and at each scheduled post Baseline visit will be provided for hematology and serum chemistry to assess changes in laboratory values from Baseline to each on-study evaluation from the central or local labs. The subjects meeting Hy's law criteria (defined as AST or ALT ≥ 3 xULN together with total bilirubin ≥ 2 xULN at any timepoint) will be summarized by visit.

Urine chemistry and urinalysis results will not be summarized but will be provided in a data listing.

All clinical laboratory data (including central and local) will be presented in by-subject data listings.

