APPENDIX A. DATA PRESENTATION CONVENTIONS:

Unless otherwise specified, the baseline value for analyses of all parameters is defined as the last non-missing value prior to the first administration of investigational product.

For categorical variables, the number and percentage of subjects within each category of the parameter, including a category for missing data, will be presented. Percentage calculations will be based on the analysis population, unless otherwise specified.

For continuous variables, summary statistics will include the number of subjects and the mean, standard deviation (SD), standard error of the mean (SEM), median, 25th and 75th quartiles, minimum, and maximum values.

All statistical analyses will be performed using SAS statistical software Version 9.4 or higher unless otherwise noted.

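### The same laboratory analytes carry three baseline rules (last pre-dose value, mean of all pre-dose values, Day 1), which can give different results when more than one pre-dose value exists

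*SAP*

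**What the plan says.** Three rules are in force.

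- **Last value before first dose.** Protocol 15.3 has baseline "defined as the last assessment performed before the first dose of investigational product in Study 977-311", and protocol 15.4 and the opening of 15.3.2 say the same. For efficacy, SAP 9.1 states: "Baseline is defined as the last assessment performed before the first dose of investigational product in Study 977-311, unless otherwise specified". SAP 5.1 gives this as the general rule. SAP Appendix A agrees but drops the limit to this study: "the baseline value for analyses of all parameters is defined as the last non-missing value prior to the first administration of investigational product".
- **Mean of pre-dose values.** SAP 10.3, for laboratory parameters: "Baseline is defined as the mean of all available evaluations prior to the first administration of investigational product". Protocol 15.3.2, in the same paragraph that begins with the last-value rule: "Baseline is defined as the mean of all available evaluations before treatment (except for lipoprotein assessments where Baseline will be Day 1").
- **Day 1.** SAP 5.1: "For subjects under protocol amendment 2, the baseline value is defined as the evaluations on Day 1". Protocol 15.3.2 also uses Day 1 for lipoproteins and for the laboratory shift tables.

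On the meaning of Day 1, SAP 5 has study days "numbered relative to the day of the first dose of investigational product which is designated as Day 1". SAP 3.1 uses Day 1 and Day 2 as visit names and starts dosing on Day 2. SAP 11 declares no departures from the protocol's analyses.

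**The concern.** Baseline enters every change, percent-change, responder and shift table. This is a single-arm descriptive study, so change from baseline carries the interpretation. ALP, ALT, AST, GGT and bilirubin are both efficacy endpoints (SAP 9.1) and laboratory safety parameters (SAP 10.3). As written, one post-baseline result can be compared with two different baselines in the same report, and a subject can be normal at baseline in one table and high in another. Two programmers following different sentences could both claim to comply. If the choice is left until data have been seen, it becomes discretionary.

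The Day 1 sentence adds a labelling problem. The only study-day rule in the SAP makes Day 1 the dosing day, yet under the current protocol dosing takes place at the Day 2 visit, where no laboratory sample is scheduled.

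**Working it through.** The plan gives no figure to reproduce. The check compares the rules, maps the day labels, and shows when the numbers separate.

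**1. Where the rules collide**

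| Use | Rule in the SAP | Rule in the protocol |
|---|---|---|
| Efficacy: ALP, GGT, ALT, AST, bilirubin | Last value (9.1); Day 1 for amendment 2 subjects (5.1) | Last value (15.4) |
| Laboratory change tables | Mean (10.3) | Last value (15.3); last value and mean (15.3.2) |
| Lipoproteins | Mean (10.3, no exception) | Day 1 (15.3.2) |
| Laboratory shift tables | Mean (10.3) | Day 1 (15.3.2) |

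The lipoprotein and shift-table rows also differ between the two documents, which SAP 11 does not record.

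**2. Day labels.** Inputs: first dose on protocol day d, with d from 2 to 7 (protocol 7.1.2, Day 2 visit window); SAP 5 sets the dosing day to Day 1 and the preceding day to Day -1, with no Day 0. The Day 1 visit draw then falls on SAP day 1 - d:

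- d = 2 gives Day -1
- d = 7 gives Day -6

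No scheduled laboratory value falls on SAP Day 1. Protocol Table 3 and section 9.7.2.2 list no blood sample at the Day 2 visit, only a review of Day 1 results.

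**3. When the rules agree.** Table 3 schedules one pre-dose laboratory draw, at the Day 1 visit. If that is the only eligible value, last = mean = Day 1 visit, and the difference is zero.

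**4. When they diverge: a repeat before dosing (hypothetical).** Under protocol 9.7.2.2, out-of-range Day 1 results go to case-by-case review, and 9.7.3 permits repeat assessments. Assume ALP 220 U/L at the Day 1 visit and 200 U/L on repeat.

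- Last = 200; mean = (220 + 200)/2 = 210; Day 1 visit = 220.
- A later value of 200 is a change of 0/200 = 0%, -10/210 = -4.8%, or -20/220 = -9.1%.
- The cut-off for a 40% reduction is 0.6 x 200 = 120 U/L under SAP 9.1, or 0.6 x 220 = 132 U/L under the SAP 5.1 Day 1 sentence.

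SAP 5.5 restricts analyses to scheduled visits, so whether the repeat may serve as baseline at all is also unsettled.

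**5. When they diverge: several earlier values averaged in (hypothetical).** Assume the last ALP is L = 200 U/L and k earlier values at r times that level. Mean baseline = (k x r x L + L)/(k + 1). Take a later value of 120 U/L, a 40.0% fall from the last value.

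| k | r | Mean baseline (U/L) | Change at 120 U/L |
|---|---|---|---|
| 3 | 0.9 | (540 + 200)/4 = 185 | -65/185 = -35.1% |
| 1 | 1.25 | (250 + 200)/2 = 225 | -105/225 = -46.7% |
| 3 | 1.5 | (900 + 200)/4 = 275 | -155/275 = -56.4% |

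The 40% fall in the efficacy table would thus appear as about 35% to 56% in the laboratory table. The values of L, k and r are assumptions, since the documents state no pre-dose ALP for this study.

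**The case against.** The strongest defence has four parts.

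- **Day 1 means the visit.** The numbering in SAP 5 is introduced for data listings, SAP 3.1 uses Day 1 and Day 2 as visit names, and the sentence in SAP 5.1 is tied to the version that evidently added the Day 2 visit. This is the probable meaning. It still has to be inferred: SAP 5.1 does not say visit, and the protocol calls its current text Version 2.0, not amendment 2.
- **There is one scheduled pre-dose draw.** With SAP 5.5 limiting analyses to scheduled visits, the mean is a mean of one. This stands as the zero-effect case. However, SAP 10.3 asks for all available evaluations, and a Day 1 exception for lipoproteins alone (protocol 15.3.2) would be pointless if Day 1 were the only value.
- **The general rule yields where another is specified.** That clause in SAP 5.1, 9.1 and Appendix A lets SAP 10.3 set its own laboratory baseline. It does not stop one analyte having two baselines in one report. It cannot resolve protocol 15.3.2, which has no such clause.
- **Nothing says parent-study values will be imported.** That is correct, and the SAP's scope is Study 977-311. But SAP 10.3 omits the study limit that SAP 5.1 and 9.1 include, and subjects enter while taking parent-study product, so earlier values exist and are not clearly excluded.

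The study also has one arm and no hypothesis, so no test or error rate is affected. That lowers the severity but leaves the inconsistency in the tables.

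**Conclusion.** The concern holds as a conflict of definitions that should be fixed before any data snapshot. Its effect is zero if each subject has only the Day 1 visit draw and Day 1 means that visit. Otherwise it depends on how many pre-dose values are eligible and how far they differ. The illustrations above rest on assumed values and are not estimates for this trial.

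Two stronger conclusions are tempting but not supported.

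- A reader might infer that amendment 2 subjects have no baseline, because SAP Day 1 is the dosing day and no sample is drawn then. That follows only from a literal reading of SAP 5; the visit meaning is more likely. It is an ambiguous label, not evidence that baselines will be missing.
- A reader might take ALP levels of about 315 and 119 U/L from protocol 5.4.3 and conclude that averaging in parent-study values would make an unchanged subject appear to improve by 19% to 35%. The protocol states neither level. They are back-calculated from the LS mean reductions in one arm of Study 747-213 (196.4/0.623 = 315; 315 - 196 = 119). An absolute LS mean change divided by a percent LS mean change is not a mean baseline. The percentages also need assumed counts of averaged values, and no text says parent-study values will be used.

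**What to change.** Use one baseline for all parameters: the last non-missing value before the first FDC dose in Study 977-311, normally the Day 1 visit. State that repeat or unscheduled pre-dose draws are eligible despite SAP 5.5.

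- SAP 10.3: delete the mean sentence.
- SAP 5.1: delete or replace the Day 1 sentence, or write Day 1 visit.
- SAP Appendix A: add the limit to Study 977-311.
- SAP 5: separate visit labels from relative study day, for example by calling the latter treatment day.
- Protocol 15.3.2: align at the next amendment. Until then, record the difference in SAP 11.

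The cost is small wording and programming edits to the SAP. The protocol edit can wait for an amendment made for other reasons. Protocol section 15 requires the SAP to be final before any snapshot, so that is the deadline.

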5.2. Partial Dates

If only a partial date is available and is required for calculation, the following standards will be applied:

- Diagnostic Date (e.g., PBC diagnostic date)
 - For missing day only – Day will be imputed as the first day of the month (i.e., 1).
 - For missing day and month – Day and month will be imputed as the first day of the year (i.e., 1 January).
- Start Dates (e.g., event date, AE onset date, or start date of medication)
 - For missing start day only – Day will be imputed as the first day of the month (i.e., 1) with the following exception: if the partial date falls in the same month and year as the date being used in the calculation (e.g., first dose date, informed consent date), then the partial date will be imputed to equal the date being used for the calculation.
 - For missing start day and month – Day and month will be imputed as the first day of the year (i.e., 1 January) with the following exception: if the partial date falls in the same year as the date being used in the calculation (e.g., first dose date, informed consent date), then the partial date will be imputed to equal the date being used for the calculation.
 - Imputed start dates must be prior to the stop date. Otherwise, the start date will be further imputed to be the same as the stop date.
- Stop Dates (e.g., AE resolution date or stop date of medication)
 - For missing stop day only – Day will be imputed as the last day of the month (i.e., 28, 29, 30, or 31).
 - For missing stop day and month – Day and month will be imputed as the last day of the year (i.e., 31 December).
 - Imputed stop dates must be on or after the start date. Otherwise, the stop date will be further imputed to be the same as the start date.

5.3. Data Conventions

The precision of original measurements will be maintained in summaries, when possible.

For tables where rounding is required, rounding will be done to the nearest round-off unit. For example, when rounding to the nearest integer, values $\geq XX.5$ will be rounded up to $XX+1$ (e.g., 97.5 will round up to 98), while values $< XX.5$ will be rounded down to XX (e.g., 97.4 will round down to 97).

Percentages based on frequency counts will be based on available data, and denominators will generally exclude missing values, unless otherwise stated. For frequency counts of categorical variables, categories whose counts are zero will be displayed for the sake of completeness. For example, if none of the subjects discontinued due to “lost to follow-up,” this reason will be included in the table with a count of 0. Percentages based on frequency counts will be presented as a whole number (no decimal places), and values less than 1% will be presented as “<1%.” Values less than 100% but that round up from 99.5% to 100% will be presented as “>99%.”

Quantitative laboratory tests containing less than ($<$) and greater than ($>$) symbols are test results that are below and above quantifiable limits, respectively. In order to retain these values for analysis purposes, the following imputations will be done within the analysis datasets:

For laboratory test results that are below the quantifiable limit:

$$\text{Imputed laboratory results} = (\text{numeric portion of the result}) \times 0.9$$

For laboratory test results that are above the quantifiable limit:

$$\text{Imputed laboratory results} = (\text{numeric portion of the result}) \times 1.1$$

Standard Quantitative laboratory tests containing less than ($<$) and greater than ($>$) symbols are test results that are below and above quantifiable limits, respectively. In order to retain these values for analysis purposes, the following imputations will be done within the analysis datasets:

For laboratory test results that are below the quantifiable limit:

$$\text{Imputed laboratory results} = (\text{numeric portion of the result}) \times 0.9$$

For laboratory test results that are above the quantifiable limit:

$$\text{Imputed laboratory results} = (\text{numeric portion of the result}) \times 1.1$$

5.4. Calculations

Variables requiring calculation will be derived using the following formulas:

- Days – A duration expressed in days between one date (*date1*) and another later date (*date2*) will be calculated using the following formulas:
$$\text{duration in days} = \text{date2} - \text{date1} + 1, \text{ where } \text{date1} \geq \text{first dose date}$$
$$\text{duration in days} = \text{date2} - \text{date1}, \text{ where } \text{date1} < \text{first dose date}$$
- Months – A duration expressed in months is calculated as the number of days divided by 365.25/12 (approximately 30.4)
- Years – A duration expressed in years between one date (*date1*) and another date (*date2*) is calculated using the following formulas:

duration in years= (date2 – date1 + 1)/365.25, where date1 ≥first dose date

duration in years= (date2 – date1)/365.25, where date1 <first dose date

- Age of diagnosis – Age of diagnosis is calculated as the number of years from the imputed year of birth (*DOB*) to the year of diagnosis. The imputed year of birth is derived as year of inform consent – age. The following formula is used:

age (years)= year of diagnosis – imputed year of DOB + 1

- Height – Height entries made in inches are converted to centimeters using the following formula:

height (cm)= height (in) × 2.54

- Weight – Weight entries made in pounds are converted to kilograms using the following formula:

weight (kg)= weight (lb) / 2.2046

- Temperature – Temperature entries in degrees Fahrenheit are converted to degrees Celsius using the following formula:

temp (degrees Celsius) =5 / 9 × (temp [degrees Fahrenheit] – 32)

- Body Mass Index (BMI) – BMI is calculated using height (cm) and weight (kg) using the following formula:

[figure not shown]
BMI (kg/m²) =weight (kg) / ([height (cm)/100]²)

- Change from Baseline – Change from Baseline will be calculated as:

Change=post Baseline value – Baseline value

- Percentage change from Baseline – Percentage change from Baseline will be calculated as:

Percentage change from Baseline= ([post Baseline value – Baseline value] / Baseline value) × 100

Note: TRANS= ALT ratio to upper limit. When ALT is missing, TRANS=AST ratio to upper limit.

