7. DEMOGRAPHICS AND BASELINE DISEASE CHARACTERISTICS

7.1. Demographics and Baseline Characteristics

Demographic variables will include the following:

- Age at informed consent (Continuous and Categorical (<65 and ≥65))
- Sex (Male and Female)
- Race (American Indian or Alaska Native, Asian, Black or African American, Native Hawaiian or Other Pacific Islander, White and Other)
- Ethnicity (Hispanic or Latino, Not Hispanic or Latino, Not reported)
- Geographic Region

Other Baseline characteristics will include the following:

- Weight (kg)
- Height (cm)
- BMI (kg/m²)

Key liver function test results as a continuous variable and categorized as follows:

- ALP (U/L)
- Total Bilirubin (μmol/L)
- Albumin (g/L)
- Use of UDCA (Yes/No)

- Total daily dose of UDCA (mg) as determined using the last dosage reported prior to the first dose

Demographics and Baseline characteristics will be summarized and presented in overall for LTSE and PK populations. For categorical variables, the number and percentage of subjects within each category, including a category for missing data, will be presented. For continuous variables, summary statistics will include the number of subjects and the mean, SD, SEM, median, 25th and 75th quartiles, minimum, and maximum values. No inferential statistical comparisons will be performed.

All demographic and Baseline characteristics data will be presented in by-subject data listings.

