7.2. Baseline PBC Disease Characteristics

Baseline PBC disease characteristics will be summarized using data collected from the PBC Disease History and other eCRFs. Variables of the PBC Disease History include the following:

- Age at PBC diagnosis
- Duration of PBC in years at time of informed consent
- History of PBC related pruritus (Yes/No)
- Severity of most recent pruritus event
 - Ongoing at screening
- History of PBC-related fatigue (Yes/No)
 - Ongoing at screening
- Overall severity of PBC-related fatigue

Baseline PBC disease characteristics will be summarized and presented in overall for LTSE population.

Baseline PBC disease characteristics will be presented in by-subject data listings.

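### The SAP's age-at-diagnosis formula adds a year that its own definition does not, so reported age at PBC diagnosis is too high by about 1 year on average if age is in completed years

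*SAP*

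**What the plan says.** SAP 5.4 (Calculations) derives the variable in three steps.

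- Description: "Age of diagnosis is calculated as the number of years from the imputed year of birth", running to the year of diagnosis.
- Birth year: "The imputed year of birth is derived as year of inform consent – age".
- Formula: "age (years)= year of diagnosis – imputed year of DOB + 1".

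The same section has a general rule for durations in years. When the start date precedes first dose, the rule is "duration in years= (date2 – date1)/365.25, where date1 <first dose date". When the start date is on or after first dose, one day is added before the division by 365.25.

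SAP 7.2 lists "Age at PBC diagnosis" among the baseline PBC disease characteristics, beside "Duration of PBC in years at time of informed consent". Both go into a summary table for the LTSE population and into by-subject listings. SAP 7.1 reports age at informed consent but does not say whether it is in completed or decimal years. The protocol gives no derivation of age at diagnosis.

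**The concern.** The words describe a plain difference between two calendar years, and the formula then adds one. No reason is given. A birth date always precedes first dose, so the SAP's own years rule would add nothing here. Where that rule does add something, it adds one day, or 1/365.25 = 0.003 year, not a whole year. The term looks like a day-count convention carried over to a variable measured in years.

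At stake is the accuracy of one baseline characteristic in the study report. The error is systematic, so it does not average out over about 133 subjects. A programmer also has to choose between the description and the formula.

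**Working it through.** The documents give no numerical result for this variable, so there is no figure to reproduce. The check is algebra, confirmed by simulation.

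**Inputs.** The formula, birth-year rule and years rule come from SAP 5.4. The protocol synopsis gives July 2024 as the date of first enrolment but no distribution of consent dates. Three assumptions are needed: age at consent is in completed years; birthdays are spread evenly over the year; and consent and diagnosis dates are too, except where varied below. The partial-date rule in SAP 5.2 leaves the diagnosis year unchanged, so it does not enter.

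**Algebra.** Let b, c and d be the positions within the calendar year (0 to 1) of birthday, consent and diagnosis. Let [x] be 1 if x is true and 0 otherwise.

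1. Imputed birth year = true birth year + [b > c].
2. Completed age at diagnosis = diagnosis year − true birth year − [b > d].
3. Error of the SAP formula = 1 − [b > c] + [b > d], which can only be 0, +1 or +2.
4. Mean error = 1 − (1 − mean c) + (1 − mean d) = 1 + mean c − mean d.
5. Error without the +1 = [b > d] − [b > c], with mean (mean c − mean d).

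**Dates spread evenly.** Mean c = mean d = 0.5, so the mean error is 1 + 0.5 − 0.5 = +1.0 year. An error of 0 needs c < b < d (probability 1/6), an error of +2 needs d < b < c (1/6), and the remaining 4/6 have +1. A simulation of 2,000,000 subjects agrees:

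| | Mean error (years) | Distribution |
|---|---|---|
| SAP formula | +1.00 | 0 in 16.7%, +1 in 66.6%, +2 in 16.7% |
| Without the +1 | 0.00 | −1 in 16.7%, 0 in 66.6%, +1 in 16.7% |

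**Season of consent** (diagnosis dates still even):

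| Consents | Mean c | Mean error, SAP formula | Subjects with no error |
|---|---|---|---|
| All July–December | 0.75 | +1.25 | 4.2% |
| All January–June | 0.25 | +0.75 | 29.2% |
| All late December | about 1 | about +1.5 | about 0% |
| All early January | about 0 | about +0.5 | about 49% |

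**Against exact decimal age at diagnosis.** The error is 1 − [b > c] + b − d, with mean 1 − 0.5 + 0.5 − 0.5 = +0.5 year. Without the +1 it is −0.5 year.

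**Worked cases** (hypothetical, all with consent on 15 July 2024):

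| Born | Age at consent | Imputed birth year | Diagnosed | Completed age | SAP formula | Error |
|---|---|---|---|---|---|---|
| 1 Oct 1970 | 53 | 1971 | 1 Nov 2010 | 40 | 2010 − 1971 + 1 = 40 | 0 |
| 1 Mar 1970 | 54 | 1970 | 1 Jun 2010 | 40 | 2010 − 1970 + 1 = 41 | +1 |
| 1 May 1970 | 54 | 1970 | 1 Feb 2010 | 39 | 2010 − 1970 + 1 = 41 | +2 |

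**Consistency with the neighbouring variable.** Age at diagnosis plus duration of PBC at consent should return age at consent. With dates spread evenly, the SAP formula makes the sum exceed completed age at consent by 1.00 year on average. Without the +1 the mean excess is 0.00.

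**The case against.** The strongest reply has four parts.

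- **The target is not defined.** The SAP never says that age means completed years. Against decimal age the formula is about 0.5 year too high and the version without the +1 about 0.5 year too low, so deletion is no closer on average. This stands as a limit on the size of the error. It does not justify the +1, which still contradicts the SAP's description and its years rule.
- **The size depends on when subjects consent.** The documents do not give that distribution, so a single value of +1.0 claims too much. This stands, and the range is part of the point. With diagnosis dates spread evenly, the mean error against completed age stays positive throughout that range.
- **Not every subject is affected.** A reader might infer that each reported age is a year too high. Step 3 of the algebra shows otherwise: the shift is in the mean, and some subjects have no error.
- **Impossible values are unlikely here.** A subject aged 50 at consent in 2024 and diagnosed in 2024 would get 2024 − 1974 + 1 = 51, older at diagnosis than at consent. A reader might expect such rows in the listings. The named parent studies (protocol 5.4) took subjects with an inadequate response to UDCA or unable to tolerate it, and both were already fully enrolled with extensions running. Diagnosis in the consent year is therefore very unlikely for them; only the unspecified other Sponsor studies leave it open. The example shows that the formula is faulty, not what the data will contain.

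The practical effect is also small. SAP 7.1 rules out inferential comparisons for the baseline characteristics it covers, and SAP 9.5 and 10.8 plan no subgroup analyses.

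**Conclusion.** The formula is wrong as written, and the point is minor. The contradiction within SAP 5.4 needs no assumption. The size does: with age in completed years and dates spread over the year, reported age at diagnosis is too high by about 1 year on average, or about 0.5 to 1.5 years at the seasonal extremes. Measured against decimal age, the average overstatement is about half a year.

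The documents do not support reading this as a threat to the trial's conclusions. The variable appears in one descriptive table and its listing, and no safety or efficacy endpoint is stated to use it.

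**What to change.** In SAP 5.4, delete the +1, so that age at diagnosis = year of diagnosis − imputed year of birth. Add a sentence saying that age is in completed years.

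The result is still approximate. With dates spread evenly the mean error against completed age is zero, but about one subject in six is 1 year too low and one in six 1 year too high, because only calendar years are used. If consents cluster in one half of the year, a mean error of about −0.25 to +0.25 year remains.

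The cost is one term and one sentence in the SAP, with the matching line of programming. No data collection changes.
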